4.3 Exit Criteria

Subjects will exit the study if any of the following conditions exist:

1. Subject voluntarily withdraws from the study.
2. Subject death.
3. Subject acquires any of the listed exclusion criteria.
4. Subject completes the protocol.
5. Subject is non-compliant with the study protocol. Subject non-compliance is defined in Section 5.5.

Subjects exiting the study prior to completion of the protocol will be withdrawn as per Section 4.5.

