4.5 Early Withdrawal of Subjects

4.5.1 When and How to Withdraw Subjects

Subjects may withdraw from the study at any time by withdrawing their consent. They must agree to be contacted (for safety reasons) for survival data. Subjects who do not adhere to the study drug dosing may also be withdrawn from the study to preserve the data collection.

If the subject withdraws from the study, it will be recommended to titrate off the medication per the chart depending on current dose.

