5.5 Subject Compliance Monitoring

Compliance will be monitored by having the parents of the subject bring any unused drug back to Gillette Children's Specialty Healthcare each time they visit for the study. Amount of unused drug will be measured by the pharmacy before the subjects can get their next supply of study drug. Subjects will also be called every two weeks to assess any AEs and any positive effects subjects are experiencing. They will be asked how the customized drug plan for them is working. If a subject is found to be noncompliant with the study drug, the subject will be withdrawn from the study, with all withdrawal procedures followed. A subject will be defined as noncompliant if more than three days of doses of drug are missed.

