6.0 Study Procedures

Outline of procedure plan

1. Recruitment from clinics including: chronic care, neurology, gastroenterology, and pain
2. History and physical examination completed as part of routine assessment and management for chronic irritability
3. Determine if evaluation for potentially treatable causes of chronic irritability has been completed.
4. Parental consent
5. Parental questionnaire #1 and NCCPC-R rating 3 typical irritable events
6. Randomization: gabapentin or placebo
7. Titration schedule
8. Day 6 — phone call by study staff (or closest week day)
9. Day 13 — NCCPC-R, questionnaire #2, and phone call follow-up (or closest week day)
10. Day 24 — NCCPC-R, questionnaire #2, and phone call follow-up (or closest week day)
If no improvement (dose 40 mg/kg/day) begin taper early(step #11) and set up visit with Research Coordinator (Step #12)
11. Day 29 — Begin medication taper
12. Day 34 to 38 — Family comes in to meet with the Research Coordinator. Subject is weighed. Perceived benefits and side effects of the drug are discussed. Report any concerns to the PI, if any. Subject is provided new drug at this visit. The old bottle will be taken back, along with the dosing chart. Remaining drug will be measured.
13. Day 38 — Crossover
14. Repeat steps 7 —11
15. At completion Research Coordinator contacts family by telephone to discuss perceived benefits/side effects of round 2 drug. Reports concerns to PI, if any

Parents complete one questionnaire #1, four questionnaires #2, and six NCCPC-R

Questionnaire # 1: includes 60 questions that require identifying the appropriate response from the items listed and 5 questions that require a written response.

Information obtained includes: frequency and duration of pain episodes along with associated gastrointestinal symptoms and sleep disturbance. The questionnaire takes approximately 15 minutes to complete.

Questionnaire #2: includes 24 questions that require identifying the appropriate response from the items listed and 2 questions that require a written response. Information obtained includes: frequency and duration of pain episodes along with associated gastrointestinal symptoms and sleep disturbance. The questionnaire takes approximately 5 minutes to complete.

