NCCPC-R: Pain behavior in nonverbal neurologically impaired children can be measured using the Non-Communicating Children's Pain Checklist-Revised (NCCPC-R).^{10, 11} The scale consists of seven domains including Vocal, Eating/Sleeping, Social/Personality, Facial Expression, Activity, Body/Limbs, and Physiological. The NCCPC-R has shown validity and reliability for everyday pain among children with developmental disabilities and was applied to study the incidence of pain in children with severe neurological impairments. Cut-off scores based on receiver operating characteristics suggest a score of 7 or greater on the NCCPC-R as indicative of pain in such children. The NCCPC-R takes approximately 5 minutes to complete.

Schedule of Events

Day	Pre-screen	Informed Consent	Medical History	Physical Exam	Phone Check	NCCPC-R	Q1	Q2
0	X	X	X	X		X	X	
6					X			
13					X	X		X
24					X	X		X
28					X			
34-37			X			X		X
38					X			
44					X			
51					X	X		X
62					X	X		X
76					X			

The Day 0 visit occurs as an office visit at the Gillette Children's Specialty Healthcare facility. A medical history and physical examination will be completed as part of routine assessment and management for chronic irritability. Determine if evaluation for potentially treatable causes of chronic irritability has been completed. The first round of drug will be dispensed. Families will be asked to mark off each dose they take out of the bottle with an X on the dosing sheet. Another visit with the research coordinator will occur once the drug has been tapered, during the washout period. During that visit, the subject will be re-weighed, the old drug bottle will be taken and the remaining drug measured, and

the old dosing sheet will be taken. Any benefits or side effects will be discussed at this visit, and the new drug bottle will be dispensed. Once drug has been tapered the second time, patients will be instructed to return the bottle when they return for their next standard of care appointment at Gillette Children's Specialty Healthcare.

Unscheduled visits

If any unscheduled visits occur due to side effects, another physical exam will be done and side effects will be recorded. Standard of care treatment will be administered for side effects. The NCCPR-C and Questionnaire #2 will be done as well.

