7.2 Statistical Methods

Simple descriptive statistics will be utilized to compare differences between the treatment and placebo groups with respect to frequency and duration of pain episodes, and frequency of gastrointestinal and sleep problems. Parent/caregiver reported questionnaires will be compared between groups. The NCCPR-R assessments will be scored and compared between groups, with a 15 point difference considered a significant difference.

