7.3 Subject Population(s) for Analysis

The subject population to be analyzed includes all protocol compliant subjects. Subjects who are not compliant with the protocol will be withdrawn as described in Section 5.5

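### Sections 7.3 and 5.5 leave no stated population of all dosed children for safety, so children who miss doses because of side effects can drop out of the tolerability result

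*SAP*

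**What the plan says.** - **Analysis population.** SAP 7.3 reads "The subject population to be analyzed includes all protocol compliant subjects" and refers noncompliant children to withdrawal under 5.5. No other population is defined for this trial. Intent to treat appears only in the abbreviation list and in the background on the postherpetic neuralgia studies (1.4).
- **Noncompliance.** SAP 5.5: "A subject will be defined as noncompliant if more than three days of doses of drug are missed". It makes no exception for side effects or a medical hold. The consequence is "If a subject is found to be noncompliant with the study drug, the subject will be withdrawn from the study".
- **Withdrawal.** SAP 4.5.1 is softer: "Subjects who do not adhere to the study drug dosing may also be withdrawn from the study". It also recommends a taper for any child who withdraws.
- **Exits.** SAP 4.3 lists voluntary withdrawal, death, an acquired exclusion criterion, completion, and "Subject is non-compliant with the study protocol. Subject non-compliance is defined in Section 5.5".
- **Side effects.** SAP 6.0: "If any unscheduled visits occur due to side effects, another physical exam will be done and side effects will be recorded". Standard care follows. No dose hold or reduction is described.
- **Methods.** SAP 7.2: "Simple descriptive statistics will be utilized to compare differences between the treatment and placebo groups". The outcomes covered are pain episodes, gastrointestinal and sleep problems, questionnaires and the pain checklist. Adverse events are not among them.
- **Safety collection.** SAP 8.1 and 8.2 require all adverse events to be recorded, up to 30 days after the last dose, with no condition on compliance.
- **Hypothesis.** SAP 2.0 states the primary hypothesis as benefit together with safety.

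**The concern.** A population chosen on compliance is an awkward base for a safety statement, because poor tolerability is itself a cause of missed doses. SAP 1.5 lists somnolence, dizziness, hostility and nausea or vomiting among the commoner risks of gabapentin, so a caregiver who skips doses for such reasons is foreseeable. Under 5.5 that child becomes noncompliant, and under 7.3 is outside the only population the plan names.

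At stake is the safety half of the primary hypothesis. An analyst who follows Section 7 literally would tabulate side effects among children who managed to stay on their doses and leave out those who could not.

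**Working it through.** The document gives no figure to reproduce on this point, so the check is mainly one of reading.

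**1. Follow one child through the rules.** The child has side effects, misses four days of doses, and the family keeps consent.
- 5.5: noncompliant, whatever the reason.
- 4.5.1 against 5.5: withdrawal is optional in one and required in the other. This does not matter here, because 7.3 selects on compliance and not on withdrawal.
- 7.3: outside the analysis population.
- 6.0: the only early taper in the procedure outline is for lack of benefit ("If no improvement (dose 40 mg/kg/day) begin taper early(step #11"). A taper after side effects comes through withdrawal under 4.5.1. Neither keeps this child in the 7.3 population.
- 8.2: the side effect is recorded.

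So the event is on file, but the child is not in the one population named for analysis. If the family had withdrawn consent instead, 7.3 does not say whether the child still counts as compliant; the point does not rest on that case.

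**2. How low the threshold is.** From the 5.2 schedule, doses per period are:
- days 1–3, one a day: 3
- days 4–33, three a day: 30 × 3 = 90
- day 34: 1
- total: 94

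Four three-dose days are 12 doses: 12/94 = 12.8% of one period, or 12/188 = 6.4% of both. Section 5.5 does not say which count applies.

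**3. When the compliant set misstates the rate.** Let p be the share of dosed children with a given side effect, f the share of affected children who become noncompliant, and g the same share among unaffected children. The rate seen in the compliant set is

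p(1 − f) / [p(1 − f) + (1 − p)(1 − g)].

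This is below p if f > g, equal to p if f = g, and above p if f < g. The direction therefore depends on how the two groups comply.

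**4. Illustration on assumed values.** None of p, f or g is in the document. Take 40 dosed children for convenience and g = 0:

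| True rate p | f = 25% | f = 50% | f = 75% |
|---|---|---|---|
| 4/40 = 10% | 3/39 = 7.7% | 2/38 = 5.3% | 1/37 = 2.7% |
| 8/40 = 20% | 6/38 = 15.8% | 4/36 = 11.1% | 2/34 = 5.9% |
| 16/40 = 40% | 12/36 = 33.3% | 8/32 = 25.0% | 4/28 = 14.3% |

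The opposite case, with p = 20%, f = 25% and g = 50%: 6 of 8 affected and 16 of 32 unaffected children remain, giving 6/22 = 27.3%, above the true 20%.

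The table has two limits. The Study Summary speaks of 40 evaluable subjects, so the number dosed may be larger. The rates are also pooled, so they say nothing about a gabapentin-versus-placebo difference.

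**The case against.** The strongest reply is that nothing in the document applies 7.3 to safety. Section 7 deals with efficacy measures, and safety has its own Section 8, which collects events from every child regardless of compliance. On that view the plan merely leaves the safety denominator unstated. This stands in part: the harm is conditional on using the 7.3 population for safety. But 7.3 is not limited to efficacy, no other population is offered, and the hypothesis to be judged includes safety.

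A reader might go further and infer any of the following, which the documents do not support:
- **That safety data on these children are lost.** They are not. Events are sought at each contact (8.2), caregivers document each dose (5.9.3), missing data must be explained on the CRF (9.3), and a serious-event report states whether treatment was stopped (8.3.1).
- **That a child with side effects has no way off the drug.** 4.5.1 gives a taper to any child who withdraws.
- **That the bias always flatters the drug.** It does so only if affected children comply less well than unaffected ones.
- **That the lack of an adverse-event exit in 4.3 is itself a defect.** It affects how an exit is labelled. The dosing chart and CRF are not shown, so one cannot say that the reason goes unrecorded.

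**Conclusion.** The point holds in a limited form. As written, the only named population excludes children who miss more than three days of doses because of side effects, while the primary hypothesis makes a safety claim and no analysis of adverse events in all dosed children is specified. If that population is used for the safety claim, tolerability will look too favourable under the assumption that affected children are less compliant than unaffected ones. That assumption is plausible for a sedating drug, but the document does not establish it.

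The size cannot be estimated. On the assumed values above, a true 20% could appear as anything from 15.8% to 5.9%; with equal compliance the distortion is zero, and with worse compliance among unaffected children it reverses. The finding does not show a bias in the gabapentin-versus-placebo contrast. It is worth correcting because the stated rule points the wrong way for safety and the correction costs almost nothing.

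**What to change.** Add to SAP 7.3: adverse events, and stops of study drug because of them, are reported by treatment received and by period for all children who received at least one dose, whatever their compliance; the protocol compliant population applies to efficacy only.

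Optionally, record the reason for missed or stopped doses on the existing dosing chart or CRF, if there is no field for it already.

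The cost is a short addition to 7.3 and one extra safety table. The 5.5 rule should stay as it is: 5.2 is a fixed-day schedule with no restart rule, so exempting doses missed for side effects would raise new dosing questions. Visits, drug supply, sample size and the efficacy population do not change.

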5.6 Prior and Concomitant Therapy

During the history and physical, it will be determined if the patient is now or has been treated with Gabapentin or pregabalin. If currently receiving Gabapentin or pregabalin, the patient will be excluded from the study. No restrictions on other medications and therapies will be placed on the patient other than the ketogenic diet, and use of Gabapentin or pregabalin.

Gabapentin Study

[figure not shown]

Figure 4. Study Drug Packaging

5.7 Packaging

The study drug or placebo will be packaged as a 34 day supply in an amber bottle with an oral syringe adapter and accompanying appropriately sized syringes. The bottles will be labeled with the subject's name, address, date, control number, expiration date, storage requirements and dosing instructions.

5.8 Blinding of Study Drug

The Gillette Children's Specialty Healthcare pharmacy will assign subjects to either the study drug or placebo as per the randomization table as described in Section 5.3. The pharmacy will prepare and label the study drug or placebo with a coded control number indicating group assignment.

5.9 Receiving, Storage, Dispensing and Return

5.9.1 Receipt of Drug Supplies

The study drug is Nuerontin (gabapentin) 250 mg/5 ml 470 ml bottle solution by Pfizer/Parke Davis Pharmaceutical Company. It will be obtained by Gillette Hospital Pharmacy commercially from McKesson Wholesaler in St. Paul, MN

5.9.2 Storage

Nuerontin Solution must be stored in a refrigerator between 2-8 °C or 36-46 °F. The commercial bottle is an amber light resistant glass container. It will be placed in a special labeled container in the refrigerator "Gabapentin Study Drug".

5.9.3 Dispensing of Study Drug

Each patient will have its own unique record with the patient's clinical information together with address, parent or care giver's name & phone. The drug is prescribed on a mg/kg basis with 22 day medication/placebo titration period, 7-day stable dosing, 9-day taper and washout. The drug or placebo will be labeled identically except for a unique control number on the label. The label will state that the drug must be kept in the refrigerator.

Each study patient will have a chart with each day dosing given in the morning, afternoon and evening be printed with the volume (ml's) to be administered. Example: a 10 kg child on day #4 needs 2.5 mg/kg (25 mg) in morning and afternoon plus a 5 mg/kg (50 mg) in evening. The dosing chart would have on day #4 to give 0.5 ml (25 mg) in the morning and afternoon plus 1 ml (50 mg) in the evening. Gabapentin solution is 250 mg/5ml or 50 mg/ml. This dosing chart is included with this application.

The total volume need for this 10 kg patient for the entire 34 day study would be less than 15 ml. We could dispense 20 ml in a 30 ml container with a oral syringe dispense cap.

The care giver would document each dose administered on this chart so we can reconcile the amount in the container plus the doses administered be the amount dispensed.

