5.2 Treatment Regimen

Doses will be given in liquid form through gastrointestinal tubes (if the child already has one) or orally. Children will be put on the following dosage regimen:

Day	Morning	Afternoon	Evening
1 - 3			5 mg/kg
4 - 6	2.5 mg/kg	2.5 mg/kg	5 mg/kg
7 - 9	2.5 mg/kg	2.5 mg/kg	10 mg/kg
10 - 12	5 mg/kg	5 mg/kg	10 mg/kg

13 - 15	5 mg/kg	5 mg/kg	15 mg/kg
16 - 18	7.5 mg/kg	7.5 mg/kg	15 mg/kg
19 - 21	7.5 mg/kg	7.5 mg/kg	20 mg/kg
22 - 28	10 mg/kg	10 mg/kg	20 mg/kg
29	7.5 mg/kg	7.5 mg/kg	20 mg/kg
30	7.5 mg/kg	7.5 mg/kg	15 mg/kg
31	5 mg/kg	5 mg/kg	15 mg/kg
32	5 mg/kg	5 mg/kg	10 mg/kg
33	2.5 mg/kg	2.5 mg/kg	10 ing/kg
34			5 ing/kg

35 - 37 off for 3 days then crossover

Weight			
Day	Morning	Afternoon	Evening
1 - 3			5 mg/kg
4 - 6	2.5 mg/kg	2.5 mg/kg	5 ing/kg
7 - 9	2.5 mg/kg	2.5 mg/kg	10
10 - 12	5 mg/kg	5 mg/kg	10 mg/kg
13 - 15	5 mg/kg	5 mg/kg	15 ing/kg
16 - 18	7.5 mg/kg	7.5 mg/kg	15 mg/kg
19 - 21	7.5 mg/kg	7.5 mg/kg	20 mg/kg
22 - 28	10 mg/kg	10 mg/kg	20 mg/kg
29	7.5 mg/kg	7.5 mg/kg	20 mg/lcg
30	7.5 mg/kg	7.5 mg/kg	15 mg/kg
31	5 mg/kg	5 mg/kg	15 mg/kg
32	5 mg/kg	5 mg/kg	10 mg/kg

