5.4 Preparation and Administration of Study Drug

The study drug and the placebo will be prepared in the Gillette Hospital Pharmacy. The study will also be registered with the Investigational Drug Service (IDS) pharmacy IDS #4109RO.

Neurontin (gabapentin) Oral Solution 250 mg/5 ml by Pfizer Labs

Appearance:	clear solution
Inactive ingredients:	glycerin, xylitol, purified water and artificial cool strawberry anise flavor.
Storage Requirements:	Must be refrigerated

Placebo formulation:

Appearance:	clear solution
Inactive ingredients:	see below
Storage Requirements:	Must be refrigerated

Placebo Ingredients

Ora Sweet Sugar Free (Paddock Labs)	0.5 ml
Strawberry Flavoring (Gallipot Labs)	0.2 ml
Licorice Flavoring (LorAnn Oils, Inc.)	0.05 ml
Raspberry Flavoring (Gallipot Labs)	2 ml
Sterile Water (Baxter)	15ml

Compound Instructions

1. Mix all flavoring ingredients and Ora Sweet Sugar Free in a prescription vial.
2. Add the sterile water and shake well.
3. Label and refrigerate with a 60 day expiration date

Stock Supply Label: Gabapentin Placebo Oral Solution

Refrigerate Control #
Exp: (60 days from compounding)

A sufficient amount would be dispensed for a 34 days' supply dependent on the weight of the patient.

The active or placebo drug will be dispensed on a randomized manner. A log of the patient name/weight/address/phone # 1 will be kept together with the control # of the active drug and placebo.

The blinded study code can only be broken upon a request of the Principal Investigator.

A dosing chart will be printed out for patient's family/caregiver for both the active drug and the placebo. Only a 34 days' supply will be dispensed at one

time: So if the placebo was dispensed for the first 34 days the next supply for 34 days (active drug) - the family would have to pick up the new supply.

The study treatment will be administered orally or via a gastrointestinal tube 3 times daily, with dose specified for the parent or guardian in a customized table for each study subject.

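### The dispensing example puts a 10 kg child's 34-day need below 15 ml; the SAP's own dosing table gives 166 ml

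*SAP*

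**What the plan says.** Section 5.2 introduces the dose schedule with "Children will be put on the following dosage regimen". The table rises in three-day steps from 5 mg/kg/day to 40 mg/kg/day, holds 40 mg/kg/day on Days 22 to 28, and steps down daily to 5 mg/kg on Day 34.

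Section 5.9.3 gives the strength: "Gabapentin solution is 250 mg/5ml or 50 mg/ml". For a 10 kg child on Day 4 it instructs the caregiver to "give 0.5 ml (25 mg) in the morning and afternoon plus 1 ml (50 mg) in the evening". It then states: "The total volume need for this 10 kg patient for the entire 34 day study would be less than 15 ml". The next sentence is: "We could dispense 20 ml in a 30 ml container with a oral syringe dispense cap".

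Two other sections set the supply rule. Section 5.4 says: "A sufficient amount would be dispensed for a 34 days' supply dependent on the weight of the patient". Section 5.7 says: "The study drug or placebo will be packaged as a 34 day supply in an amber bottle".

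**The concern.** The 34-day total in section 5.9.3 does not fit the daily volumes in the same section. Day 4 alone takes 2 ml and falls in only the second of eight dose levels, so a total under 15 ml for 34 days of a rising dose cannot be right. The suggested 20 ml fill carries the same error forward.

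The figure sits in the operative dispensing section, and it is the only per-patient fill volume in the text at hand. A pharmacy that took it literally would send the child home with a small fraction of one period's supply. Section 5.4 dispenses one 34-day supply at a time, and section 6.0 places the next dispensing at the visit on Day 34 to 38, so no refill is planned in between. The child would stop without a taper, although section 1.5 explains that doses go up and down slowly to limit side effects and withdrawal symptoms. The child would also be off treatment at the Day 13 and Day 24 assessments. Under section 5.5, more than three days of missed doses means withdrawal, and section 7.3 analyses only compliant subjects. The SAP does not say whether a supply shortfall would count as noncompliance.

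**Working it through.** **Inputs**
- Weight 10 kg and strength 50 mg/ml: section 5.9.3.
- Daily doses: section 5.2. Some units in the table are garbled by text extraction, but the numbers are legible and the series is regular.

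**The plan's own daily figure.** Day 4: (2.5 + 2.5 + 5) mg/kg × 10 kg ÷ 50 mg/ml = 2 ml. This reproduces the example's 0.5 + 0.5 + 1 ml, so weight and strength are read as intended.

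**The 34-day total.** Volume (ml) = sum of daily mg/kg × 10 ÷ 50.

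| Days | mg/kg/day | Days × dose (mg/kg) | Cumulative ml, 10 kg |
|---|---|---|---|
| 1–3 | 5 | 15 | 3 |
| 4–6 | 10 | 30 | 9 |
| 7–9 | 15 | 45 | 18 |
| 10–12 | 20 | 60 | 30 |
| 13–15 | 25 | 75 | 45 |
| 16–18 | 30 | 90 | 63 |
| 19–21 | 35 | 105 | 84 |
| 22–28 | 40 | 280 | 140 |
| 29–34 | 35, 30, 25, 20, 15, 5 | 130 | 166 |

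Total: 420 (titration) + 280 (stable) + 130 (taper) = 830 mg/kg. Then 830 × 10 = 8,300 mg, and 8,300 ÷ 50 = **166 ml**.

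**Comparison with the stated volumes**
- 166 ÷ 15 = 11.1, so the stated upper bound is too low by a factor of about 11.
- 166 ÷ 20 = 8.3; the suggested fill covers 20 ÷ 166 = 12% of need.
- A full 30 ml container covers 30 ÷ 166 = 18%.
- The stable week alone takes 280 × 10 ÷ 50 = 56 ml, more than the container holds.
- The Day 4 volume held flat would take 2 × 34 = 68 ml.

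**When the supply would run out**
- 15 ml: end of Day 8 (9 + 3 + 3 = 15).
- 20 ml: 18 ml is used by the end of Day 9. On Day 10 the morning and afternoon doses take 1 ml each, reaching 20 ml. The evening dose needs 2 ml more.
- 30 ml: end of Day 12.

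**Attempts to recover a figure below 15 ml**
- Strength misread as 250 mg/ml: 8,300 ÷ 250 = 33.2 ml.
- One day counted per row of the dosing table: 310 mg/kg × 10 ÷ 50 = 62 ml.
- Early taper after Day 24 for lack of improvement: 84 + 3 × 8 + 26 = 134 ml.
- Weight for which 15 ml would last 34 days: 15 × 50 ÷ 830 = 0.9 kg.

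No variant for a 10 kg child gives the stated figure.

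**The case against.** The best defence is that the passage is an illustration. It treats one weight, and the fill is offered as something the pharmacy could do. Sections 5.4 and 5.7 are what bind the pharmacy, and they are right. The regimen and strength are also right, so no prescribed dose is wrong. The pharmacy also prepares a chart of every dose in ml, on which 8 ml/day would appear for Days 22 to 28 in a 10 kg child, so the mismatch would be hard to miss.

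A run-out would probably not go unnoticed for long either. Staff phone on Day 6 and Day 13, and section 5.5 adds calls every two weeks. By the Day 13 call the child would have missed the Day 10 evening dose and all of Days 11 and 12. The packaging figure and the attached dosing chart are not at hand and may give other volumes. No endpoint, sample size or analysis uses the 15 ml figure.

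All of this stands, and it limits the weight of the point. It does not make the number right. The phone calls could shorten a gap but would not prevent it. The possible withdrawal for noncompliance is unsettled in the text and adds no weight here. The placebo recipe in section 5.4, which totals 17.75 ml as listed, is not an error, because a compounding recipe can be multiplied.

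**Conclusion.** The point holds: the volume in section 5.9.3 is wrong as written. The SAP's own table, weight and strength give 166 ml, against under 15 ml stated and 20 ml suggested. The result needs no outside assumption. The example also contradicts the supply rule in sections 5.4 and 5.7.

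The practical harm is conditional. It requires the pharmacy to follow the example over those sections and no unscheduled refill to be given. If both happened, a 10 kg child would lack drug from the Day 10 evening dose. The error should be corrected because it stands in a drug-supply instruction for children, but it does not by itself threaten the trial's design or analysis.

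**What to change.** In section 5.9.3, delete the sentence giving the 34-day volume and the sentence suggesting the 20 ml fill. Alternatively, replace them with the correct example: 166 ml for a 10 kg child, or 16.6 ml/kg per 34-day period (830 ÷ 50), in a container large enough to hold it. Any allowance for spillage should be added on top and stated.

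Sections 5.4 and 5.7 need no change, since neither fixes a bottle size. The pharmacy should confirm that its bottles and its active and placebo batches are sized from the 16.6 ml/kg figure. For placebo this means about 166 ÷ 17.75 = 9.4 times the listed recipe for a 10 kg child. The cost is two corrected sentences and a check of bottle and batch sizes.
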